Heinrich's Quality of Life Scale-Client Version - Is a 21 item semi-structured interview based rating of individual's psycho-social functioning and satisfaction with various life domains.

Temple University Community Participation Scale - is a 26 item instrument measuring frequency of participation and importance of various community activities (e.g., movies, library). Test-retest reliability is .7 and internal consistency is .9.

Scales of Psychological Well-Being - is a 54-item measure rating wellbeing (from strongly disagree to strongly agree) including subscales of mastery, personal growth, purpose in life, self-acceptance, autonomy and positive relations with others. Internal consistency is .94. It has been successfully used with individuals with SMI.

Maryland Assessment of Recovery - is a 25-item scale that assesses a person's sense of recovery from mental illness across a variety of dimensions. Internal consistency is .95 and test-retest reliability is .89).

Personal Growth and Recovery Scale - (BU CPR, 2009) - is a 16-item, 4 point scale (strongly disagree to strongly agree) developed for previous Photovoice study. Items tap aspects of person's psychosocial functioning and recovery. Internal consistency is 0.94 and retest reliability is .79.

Photovoice Program Fidelity Scale - the Photovoice Fidelity Scale was developed and used in our pilot RCT study (Russinova et al., 2014). The scale includes content fidelity items specific to each of the 10 Photovoice sessions and 13 process fidelity items which are specific to the Photovoice program as a whole. All items are measured on a 4-point scale from 1, "strongly disagree" to 4, "strongly agree". All Photovoice sessions will be audiotaped and fidelity will be assessed based on review of all audio-recorded sessions.

We will use a **Demographic Questionnaire** developed by the Boston University Center for Psychiatric Rehabilitation and previously used in multiple research studies. Questions inquire about the person's demographic characteristics, such as age, race, gender, education, employment status, housing situation, and basic clinical characteristics, such as perceived physical health and use of different mental health services in the past 3 months. We are using an abbreviated version of this questionnaire at post-treatment and follow-up assessments to capture information only on time varying variables included in the questionnaire.

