Testing Effectiveness of a Peer-Led Intervention to Enhance Community Integration

NCT02508480

Statistical Analysis Plan

Date: July 24th, 2019

Statistical Analysis Plan-

Intent-to-treat analyses will be conducted on the full sample of participants, regardless of actual exposure to the Photovoice program. Based on our pilot RCT study of Photovoice we are confident that majority of participants randomized to the Photovoice group will receive the intervention. However, if significant rates of non-exposure occur, we will also conduct separate analyses on treatment exposed participants. The intent-to-treat sample will include all participants for whom we have baseline data. It assumes that participants who are not exposed to the Photovoice program are not also study dropouts, and thus the analyses will include all available study participants. These analyses are the primary gauge of the effectiveness of the Photovoice program. If dropout rates from the Photovoice group exceed 20% we will explore the question of treatment effectiveness for those who participated in the Photovoice program. Participants will be classified based on their level of participation, with "exposure" defined as attendance at more than one-half of the 10 sessions (6 or more), with parallel analyses comparing the exposed Photovoice group with SAU. We will test the following primary hypotheses:

Hypothesis 1: Compared to SAU, clients randomized to the Photovoice program will demonstrate significantly greater improvements at post-treatment and 3- and 6-month follow-ups in their capacity to resist public prejudice and discrimination, including reduced self-stigma and perceived stigma, and increased proactive coping with public prejudice and discrimination (e.g., confronting prejudicial and discriminatory attitudes and behaviors). We will test this hypothesis by using the total score on the Internalized Stigma of Mental Illness Scale⁷⁸ and on the Stigma Scale⁹³, and the sum of the two proactive coping subscales on the Coping with Stigma Scale (Educating Others, Challenging Others)⁹² and fitting covariance pattern models (using SAS PROC MIXED) and examining time (baseline, post-treatment, 3- and 6 month follow-ups), group, and the group by time interaction effects.

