Hypothesis 2: Compared to SAU, clients randomized to Photovoice will show significantly greater improvements at post-treatment and 3- and 6- month follow-ups in community functioning and integration. The scores on the Temple University Community Participation Scale will be used as measures of community integration.

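### Two primary hypotheses rest on at least four scores, with no stated alpha, rule for combining scores or multiplicity control

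*SAP*

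**What the plan says.** The SAP introduces its hypotheses with "We will test the following primary hypotheses".

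- **Hypothesis 1.** Photovoice participants "will demonstrate significantly greater improvements at post-treatment and 3- and 6-month follow-ups", with the constructs joined as "including reduced self-stigma and perceived stigma, and increased proactive coping with public prejudice and discrimination". It names three scores: the Internalized Stigma of Mental Illness total, the Stigma Scale total, and the sum of the two proactive coping subscales. Covariance pattern models are fitted, and the effects to be examined are time, "group, and the group by time interaction effects".
- **Hypothesis 2.** It claims "significantly greater improvements at post-treatment and 3- and 6- month follow-ups in community functioning and integration". Its measure is given as "The scores on the Temple University Community Participation Scale will be used as measures of community integration". No model for it appears in the available text.

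Protocol section 7 repeats the same domains as primary, separates them from secondary wellbeing and recovery outcomes, and sets no order among them. Neither document, as available, states an alpha, an any-or-all rule, a hierarchy or an adjustment.

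**The concern.** Four or more scores carry the primary claim, and nothing says how they combine. Suppose one score is significant and three are not. The SAP's wording would allow this to be reported as a positive primary finding. It would equally allow it to be called a failure, because the constructs are joined by 'and'. That choice could be made after the results are known. If one significant score is enough, the chance of a spurious primary finding is well above the nominal 5%. If all are needed, the trial is held to a much harder standard than a single test at 96 per arm.

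The list of scores is also slightly loose. The Temple scale is described in Protocol section 7 as "measuring frequency of participation and importance of various community activities", and the SAP refers to its scores in the plural. Hypothesis 2 names community functioning, and the protocol has an interview rating "psycho-social functioning and satisfaction with various life domains", but the SAP does not link the two. Within Protocol section 7, proactive coping is among the primary hypotheses but absent from a later parenthetical list of primary outcomes. Four is therefore the minimum count.

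**Working it through.** **The plan's own figure.** The only related number is the sample size: 3 clubhouses × 4 cohorts × 16 = 192, or 96 per arm. This is recruitment arithmetic. No alpha, power, effect size or SD accompanies it, so there is no statistical figure to reproduce.

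**Inputs.** From the SAP: 3 scores (Hypothesis 1) + at least 1 (Hypothesis 2) = at least 4. Assumed: two-sided 0.05 per test, one deciding test per score, no true effect, equal correlation between outcomes of 0 to 0.7.

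**Error if any one score suffices.** Independent scores: 1 − 0.95^k. Correlated scores: 400,000 multivariate normal draws.

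| Scores | Correlation 0 | 0.5 | 0.7 |
|---|---|---|---|
| 4 (both hypotheses) | 1 − 0.95^4 = 18.5% | about 15.5% | 13.0% |
| 3 (Hypothesis 1) | 1 − 0.95^3 = 14.3% | 12.5% | 10.9% |

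I repeated this with a 3-degree-of-freedom chi-square per score, the form of the group-by-time test over four assessments, with each of the three components correlated 0.7 across scores. The result is 13.5% for four scores and 11.3% for three. With independent scores the formula is unchanged. The 13-19% and 11-14% ranges therefore do not depend on which of these two kinds of test decides.

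**If every score must succeed.** With no true effect, all four are significant in under 1% of draws at correlations up to 0.7, so error is not inflated. Power depends on figures the documents do not give. For all four scores at all three visits, with 96 per arm, no loss or clustering and outcome correlation 0 to 0.7:

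| Effect | Time correlation | Power |
|---|---|---|
| 0.2 SD | 0.6 | below 0.1% to 3% |
| 0.3 SD | 0.6 | 6-24% |
| 0.4 SD | 0.6 | 49-66% |
| 0.5 SD | 0.6 | 90-93% |
| 0.3 SD | 0.8 | 50-67% |

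**Power cost of Holm at its strictest step, 0.05/4 = 0.0125.** Assumed: 96 per arm, time correlation 0.6, the same effect at all three visits, no loss or clustering.

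*Averaged baseline-adjusted contrast.* Variance factor (1 + 2×0.6)/3 − 0.6² = 0.373; SE = sqrt(0.373 × 2/96) = 0.0882 SD.

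| Effect | z = effect/SE | Power at 0.05 | Power at 0.0125 |
|---|---|---|---|
| 0.2 SD | 2.27 | 62% | 41% |
| 0.3 SD | 3.40 | 92.5% | 82% |
| 0.4 SD | 4.54 | 99.5% | 98% |

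*Group-by-time, 3 degrees of freedom.* Noncentrality = (96/2) × 0.75 × effect²/(1 − 0.6). At 0.3 SD this is 48 × 0.75 × 0.09/0.4 = 8.1, so power goes from 66% at 0.05 to 45% at 0.0125.

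**The case against.** **Group-by-time is the natural test of Hypothesis 1.** This stands. It is the only listed effect that tests differential change from baseline, and most readers would take it as the test. A reader might infer that a positive result is wholly undefined. The documents do not support that: what is open is the significance level and how the scores combine. The test itself needs only confirming.

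**'And' may mean that all must succeed.** It may, but no rule says so. A reader might add that the trial would then be hopelessly underpowered, citing the 6-24% row. That row is one slice of a range from near zero to above 90%, and the documents give nothing to select it.

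**Phase II, separate constructs.** Protocol section 22 describes a low-risk Phase II trial, and distinct constructs can be reported separately. This makes Holm one acceptable choice among several. It does not remove the need for a rule, since the SAP words its hypotheses as significance claims and treats the intent-to-treat analyses as the main measure of effectiveness.

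**Incomplete text.** One passage was removed, and the available SAP ends after the Hypothesis 2 measure. The omission is therefore claimed only for the text available.

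**Conclusion.** The point holds for alpha, the combination rule and multiplicity control. Run at a conventional two-sided 0.05 per score, a primary claim resting on any one of four scores has a 13-19% chance of being false when nothing works (11-14% for Hypothesis 1 alone). This rests on the assumed level, one deciding test per score and outcome correlation 0.7 to 0.

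Two other inferences go further than the documents allow:

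- Counting benefit only would halve these rates to roughly 6.5-10%. That needs a directional contrast per score, and the listed group-by-time test has no direction.
- Counting four scores at three visits as 12 separate chances gives 1 − 0.95^12 = 46% if independent. The SAP does not say that a single visit would suffice.

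The Temple score and the quality-of-life interview need clarification only. Overall this is a cheap improvement, not a flaw that undermines the design.

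**What to change.** Add one SAP paragraph that:

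1. sets a two-sided familywise alpha of 0.05;
2. lists the primary scores, saying which Temple score counts and whether the quality-of-life interview is among them;
3. confirms one deciding treatment test per score: either the group-by-time effect already listed, or one pre-named Photovoice-SAU contrast from the same model;
4. applies Holm across those scores and claims only the ones that survive;
5. reports visit-specific contrasts with confidence intervals as supportive.

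A contrast averaged over the three post-baseline visits is an option, not a requirement. It changes the visit-by-visit wording and dilutes an effect confined to one visit. A fixed sequence or an explicit all-must-succeed rule would also close the gap. The documents do not show whether outcome data had been seen by the SAP date; if they had, date the rule and label it accordingly.

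The cost is power per score, as tabulated above, and largest for small effects. The strictest step applies only to the smallest p-value; later steps (0.0167, 0.025, 0.05) lose less. The model and sample size do not change.

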The inclusion criteria for the study refer to individuals who are: 1) 18 or older; 2) meet the State of MA definition of SMI based on an Axis I or II DSM-IV diagnosis and impairment in at least one major area of functioning for at least 12 months; 3) currently receiving services from Riverside; 4) willing to give written informed consent to participate in the study; and 5) conversant in English. Exclusion criteria include: 1) prior exposure to Photovoice; and 2) history or existing diagnosis of intellectual disability, based on chart records. We plan to recruit approximately 50% of the study sample among individuals with primary diagnosis of schizophrenia-spectrum (schizophrenia, schizoaffective, schizopreniform) disorder. We anticipate that most of the remaining study participants will have a primary diagnosis of a major mood disorder, and that a small proportion will have other disorders. This sample profile is reflective of the individuals served at Riverside clubhouses and by CBFS teams, since both programs are funded by the MA DMH and all recipients of services meet criteria for SMI as established by the MA DMH.

A total of 192 participants or 96 participants per group (Photovoice as the experimental condition and Services as Usual enhanced with a 60-minute peer-led group discussion as the control condition) will be recruited and randomized over a period of 36 months across the three clubhouses of Riverside Community Care where the intervention will take place. We plan to have randomization cohorts of 16 individuals per delivery of the Photovoice program at each of Riverside's three clubhouses (Needham, Norwood, and Wakefield). Given the projected sample size of 192 participants, we will have 12 randomization cohorts – 4 at each clubhouse implemented at 6-month intervals. Anticipating that not all individuals who sign the consent form complete the baseline interview and are therefore not randomized to a study group, we will enroll up to n=222 individuals in order to achieve our target sample size.

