We have been implementing the study according to this plan and have had 4 waves of recruitment at Horizon House, 5 at Neponset River House, and 3 at Eliot House for a total of 12 waves of recruitment. However, recruitment has been slowing down and we are unable to enroll approximately 16 individuals per wave as was planned. We had previously discussed a backup plan with Riverside leadership to extend the study to their clubhouse in Hopedale in the event that recruitment slowed down and we were not able to meet target recruitment. At this time, we would like to implement this plan. We have approval from the sponsor, NIMH, to proceed with this plan. The procedures at Hopedale will remain the same as they have been at the other clubhouses.

We worked with Riverside senior management to establish the non-overlapping number of clients with SMI served in the catchment areas for the three clubhouses where the Photovoice program will be offered. About 1,300 individuals with SMI are served on an annual basis in the three catchment areas (Norwood, Needham and Wakefield) where the study will be conducted; of them, approximately 900 individuals are served by the clubhouses and the CBFS teams, all of whom meet MA criteria for SMI, with approximately 50% diagnosed with a schizophrenia-spectrum disorder. Riverside treats approximately 200 new clients with SMI per year, with most being served at the clubhouses or by CBFS teams. Thus, there are an ample number of eligible participants for the study. Furthermore, in our pilot feasibility study at the Norwood clubhouse, 8 (53%) out of the 15 participants had a diagnosis of schizophrenia-spectrum disorder.

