
If an interested potential participant has a legal guardian, the guardian will be contacted by project staff and the consent process will take place with the guardian. This could occur by phone or in person. The guardian will be informed of the project details and will consent on behalf of the potential participant. We will proceed through an assent process with the participant where they are informed of the project details, informed of their guardian's involvement and consent and asked to agree to project participation and sign an assent form.

7. Research Methods and Procedures

We will conduct a randomized controlled trial (RCT) comparing the 10-week peer-led Photovoice program to services as usual (SAU) enhanced with a 60-minute peer-led group discussion session. The RCT will be conducted at a large publicly funded community mental health agency (Riverside Community Care, Inc.). The 10-session, peer-led Photovoice program, designed to empower individuals with SMI to confront public prejudice and discrimination and reduce personal stigma (self-stigma and perceived stigma), was developed and pilot tested at our Center, with primary contributions from staff with a lived experience of mental illness (see Photovoice Manuals and a Summary at Glance Table submitted as an attachment in this application.) The control SAU condition will be enhanced with a 60-minute peer-led manualized educational group session (Leaders' Guidelines and Handout for Participants are attached). The content of this session has been adapted from the Recovery Strategies module of the Illness Management and Recovery (IMR) program for the purposes of this project. It will provide participants with information about the nature of stigma and the laws in the U.S. that protect people with disabilities from discrimination. Participants will be engaged in a discussion about their use of different strategies for proactive coping with psychiatric stigma. This session will be co-led by the same peers who will be delivering the Photovoice program to the experimental group at relevant wave and study sites. An optional educational handout will be provided to participants who wish to have material in writing. In addition, participants randomized to the enhanced Services as Usual control condition will be invited to join a Photovoice group once they complete the final 6-month follow-up assessment.

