We will employ several strategies to retain participants in both the VEP sessions and in study assessments. First, we will use information from the Locator Form they will complete at baseline. We may also gather contact information from the participant's Riverside treatment team. Participants in the experimental arm will receive regular calls from the Photovoice peer leaders to encourage participation in classes. We have established a protocol for the peer leaders to call all participants the day before each Photovoice class. If they do not reach the participant, they leave a voice message. For participants who have expressed a preference for email reminders, peer leaders will send an email message the day before each class. If participants miss a class they will be encouraged to continue their involvement. Calls from the Photovoice peer co-leaders will allow an opportunity to discuss with participants any barriers to participation, such as transportation issues and to take steps to remedy those barriers.

We will implement the following protocol for contacting participants in both the experimental and control condition about upcoming assessments. The Clinical

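### The SAP's Hypothesis 1 model has no term for randomization cohort or Photovoice class, so its standard errors may be too large or too small, and the documents do not settle which

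*SAP*

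**What the plan says.** The protocol's sampling text, ahead of section 7, states "We plan to have randomization cohorts of 16 individuals per delivery of the Photovoice program" at each of three clubhouses. That makes 12 cohorts, four per clubhouse, and 96 participants per arm. Section 7 (Start Date and Duration) confirms that randomization is done wave by wave.

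The recruitment update departs from that layout. It reports "4 waves of recruitment at Horizon House, 5 at Neponset River House, and 3 at Eliot House", says that "recruitment has been slowing down and we are unable to enroll approximately 16 individuals per wave as was planned", and adds a fourth clubhouse at Hopedale. It gives no final number or size of cohorts.

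Section 7 describes a 10-session peer-led group program against usual services plus one 60-minute group session. The control session is "co-led by the same peers who will be delivering the Photovoice program to the experimental group at relevant wave and study sites".

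For Hypothesis 1 (self-stigma, perceived stigma, proactive coping), the SAP specifies "fitting covariance pattern models (using SAS PROC MIXED) and examining time" at four occasions, group, and group by time. It names no cohort, wave, class, leader or clubhouse term. A covariance pattern in such a model normally describes one person's repeated visits, and nothing in the text extends it to classmates or cohort members.

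**The concern.** Two sources of correlation are left out, and they act in opposite directions.

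- **Cohort, crossed with arm.** Randomizing within a wave should put both arms in each cohort. If cohorts differ in how much their members change, that shared part cancels from the arm comparison but stays in the model's residual. The standard error is then too large and power is lost. A cohort effect that is constant over time largely cancels from the group-by-time contrast, so the relevant part is cohort difference in change.
- **Class, nested in Photovoice.** If some classes truly do better than others, classmates' outcomes are correlated in a way that the model ignores. The standard error is then too small for a conclusion about the program beyond the classes that ran, and a borderline result is called significant too easily.

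The plan estimates neither variance, so a reader of the results could not tell which case applied.

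**Working it through.** **Layout.** 3 clubhouses x 4 cohorts x 16 = 192 = 2 x 96, which reproduces the stated sample size. An even 8:8 split within a cohort is inferred from the equal arms. If 192 is reached with 14, 16 or 18 cohorts (illustrative counts), Photovoice classes average 96/14 = 6.9, 96/16 = 6.0 or 96/18 = 5.3.

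**Assumptions.** Two-sided 0.05, average effect zero, balanced cohorts, complete data, and one visit's change score with total variance 1. Let s be the share of variance common to a cohort in both arms, r the share common to a Photovoice class (the class ICC), and m the class size.

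**Formula.** The true variance of the arm difference, relative to what a model without cohort and class assumes, is

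ratio = [(1 - s - r) + (1 - s) + m r] / 2,

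and type I error = 2 x [1 - Phi(1.96 / sqrt(ratio))].

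**Shared cohort variance only (r = 0).**
- s = 0.05: ratio 0.95, type I error 4.4%.
- s = 0.10: ratio 0.90, type I error 3.9%.

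Simulations with 12 cohorts of 16 gave 4.4% at s = 0.05 and 3.6% to 3.9% at s = 0.10.

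**Classes that truly differ.** Type I error by class ICC:

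| Class size, shared share | 0.02 | 0.05 | 0.10 |
|---|---|---|---|
| 8, none | 5.8% | 7.1% | 9.2% |
| 8, 10% | 4.7% | 5.9% | 8.0% |
| 6, none | 5.6% | 6.5% | 8.0% |
| 6, 10% | 4.4% | 5.3% | 6.8% |

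Example, first row at 0.05: (0.95 + 1 + 0.40)/2 = 1.175, and 1.96/sqrt(1.175) = 1.81, which gives 7.1%. Simulation of the first row gave 5.9%, 6.8% and 9.1%.

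**Partial attendance a.** Replace m r by m r a^2 + r a(1 - a), and the divisor 2 by 2 - r(1 - a). With m = 6, s = 0.10, r = 0.05 and a = 0.8 (assumed): (0.85 + 0.90 + 0.192 + 0.008)/1.99 = 1.95/1.99 = 0.98, or 4.8%. At r = 0.02 and 0.10 the results are 4.2% and 5.7%.

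**Break-even, 12 cohorts, classes of 8.** Clustering also lowers the expected pooled variance a little. The model's two arm variances sum to 2 - 7(2s + r)/95 in expectation, against a true value of 2 - 2s + 7r. Setting these equal gives r = 2s x 88/(7 x 96) = 0.262 s. The test is anti-conservative once the class ICC exceeds 0.013 at s = 5%, or 0.026 at s = 10%.

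**Control session.** Clustering by the control arm's single session would push further toward a standard error that is too small. With all three shares at 0.05, type I error is about 8.7%.

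**The case against.** The strongest reply is that the inflation may be slight or absent. The same peers lead both arms' groups, "fidelity will be assessed based on review of all audio-recorded sessions", and leaders are supervised throughout (protocol section 8), all of which favors uniform classes. Waves have shrunk, which weakens any class effect. Every rate above rests on assumed ICCs, and the plausible case with classes of 6 is close to nominal. If Photovoice does nothing for anyone, classes cannot differ in effect and the class error does not arise. All of this stands. It limits the size and leaves the direction open, but it does not supply the missing terms.

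Two stronger readings should be resisted.

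- A reader might take "These analyses are the primary gauge of the effectiveness of the Photovoice program" as proof that the SAP intends inference over a population of classes. In context it contrasts intent-to-treat with the analysis of exposed participants. Whether classes are treated as fixed or random remains a choice of target that the plan should state.
- A reader might take "Participants in the experimental arm will receive regular calls from the Photovoice peer leaders to encourage participation in classes" as evidence that classes differ. One calling protocol applies to the whole Photovoice arm, so it shows a difference in contact between arms and not between classes.

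It is also fair to say that a simple remedy can under-correct. Hypothesis 1 claims effects at each follow-up visit. In a simulation with class-effect standard deviations falling 1 : 0.5 : 0.25 across visits and no shared variance, a class effect held constant over visits left post-treatment type I error at 8.2% (class ICC 0.10) and 6.3% (0.05), against 10.4% and 8.0% for the SAP model. The class term therefore has to be allowed to vary by visit.

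**Conclusion.** The omission is real and should be fixed, with medium confidence in how much it matters. The documents support the statement that the Hypothesis 1 standard errors can be wrong in either direction. They do not support a claim that the test is anti-conservative, since no ICC, variance component or alpha is given. Under the assumed values, with classes of 8, type I error runs from about 3.6-3.9% (10% shared cohort variance alone) to about 9% (class ICC 0.10, none shared). The two risks are unequal: at the planned layout a class ICC of roughly a quarter of the shared share is enough to tip the test to the anti-conservative side. The recruitment update implies more, smaller and unequal cohorts, which softens the class effect and means that the balanced figures are only a guide.

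**What to change.** In the PROC MIXED model for Hypothesis 1:

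1. Add randomization cohort (site by wave, including Hopedale) and cohort by visit as fixed effects. This follows the groups in which the trial already randomizes.
2. Add a Photovoice-class random effect, or a random cohort-by-arm contrast, whose variance may differ by post-baseline visit and is bounded at zero. Use Kenward-Roger or Satterthwaite degrees of freedom, and report the class variance at each visit.
3. Pre-state a fallback for non-convergence: a visit-by-visit t test on cohort-level arm differences, which held 4.6-5.1% type I error in a balanced check.
4. Before use, test the final model by simulation at every visit under the actual cohort sizes, including post-treatment with fading class effects.
5. State whether the inference is to the program beyond the classes that ran.

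**Cost.** A few lines of text and code, plus some precision if there is no clustering. In simulation with 12 cohorts of 16 and a class effect held constant over visits, the 6-month interval was about 5% wider and power fell from 80% to 78%. Visit-specific terms may cost somewhat more and have not been costed here. The cohort-level fallback gives about 73% power. The bounded model is somewhat conservative: about 3.3% type I error in a balanced check with no clustering. Cohort is known from wave-based randomization; that class membership is on file should be confirmed.
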